### 12.9.3 Sensitivity Immunogenicity Analyses

A sensitivity analysis will be performed for the primary and secondary humoral immune response endpoints.

Applicable for sensitivity analysis for 1) 2-dose regime and 2) in addition for subjects eligible for a booster dose and receiving booster dose at day 57 or day 180. As per the immunogenicity set in section 9.5.2 with the additions:

- Subjects receiving dose 1 and dose 2 (for the separate booster sensitivity dose analysis the subjects must have received the booster dose at day 57 or day 180).
- Subjects must have no protocol deviation with impact on the immunogenicity measurement.
- Subjects in the 2-dose regime: The baseline blood sample for immunogenicity assessment and one sample at least 14 days after receiving the second dose.
- Subjects eligible and receiving a booster dose: The baseline blood sample for immunogenicity assessment and one sample at least 14 days after receiving the booster dose are available for analysis.
- Subjects must not be exposed to SARS-CoV-2 before the trial or during the trial before the endpoint evaluation.

---

For the tables the N will however be based on the immunogenicity set as per definition in section 9.5.2. The seroconversion rates are based on the n at relevant time point.

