2 SCHEDULE OF ACTIVITIES

Table 1 Schedule of Trial Assessments and Procedures

Visit Number	Primary Vaccination Period								Booster Vaccination Period								End of Trial		
	1 ^a	2	Phone contact		3	Phone contact	4	Phone contact ^b	5 ^c	Phone contact ^c	6 ^c	Prompt	7	Phone contact ^d	8 ^d	Prompt	Phone contact	9 ^w	
Visit Window (days)	n/a	-0/ +0	-0/ +0	-2/ +4	-2/ +4	-0/ +0	-2/ +4	-2/ +4	-2/ +4	-0/ +0	-2/ +4	-2/ +4	-10/ +10	-0/ +0	-2/ +4	-2/ +4	-0/ +30	-0/ +30	
Trial Day	1	2	7 ^e	15	29	30	43	57	57	58	85	120	180	181	208	270	393	393	
Anchoring	-	1	1	1	1	29	29	29	57	57	57	29	1	180	180	180	180	180	
Signed informed consent	X																		
Inclusion/exclusion criteria	X																		
Demographics	X																		
Medical history	X																		
Vaccination																			
Review of criteria for delay or cancellation of vaccination ^f	X				X				X					X ^g					
Investigational vaccine administration (including 30-minute observation)	X				X				X					X ^g					
Safety Monitoring																			
Physical examination ^h	X ⁱ				X				X					X ^g					
Symptom-directed physical examination ^h		X				X				X						X			
Vital signs ^{h,j}	X	X			X		X		X		X		X		X		X		
ECG	X																		
Diary (re)training ^k	X	X			X		X		X					X ^g					
Diary review ^k		X	X	X	X	X	X	X		X	X				X	X			
Diary reminder ^k		X		X		X	X	X	X	X				X ^g	X				
Solicited AEs ^k	X	X		X	X	X	X	X	X	X	X			X ^g	X	X			
Unsolicited AEs ^k	X	X		X	X	X	X	X	X	X	X	X	X	X	X	X	X	X	X

Visit Number	Primary Vaccination Period								Booster Vaccination Period								End of Trial	
	1 ^a	2	Phone contact		3	Phone contact	4	Phone contact ^b	5 ^c	Phone contact ^c	6 ^c	Prompt	7	Phone contact ^d	8 ^d	Prompt	Phone contact	9 ^w
Visit Window (days)	n/a	-0/ +0	-0/ +0	-2/ +4	-2/ +4	-0/ +0	-2/ +4	-2/ +4	-2/ +4	-0/ +0	-2/ +4	-2/ +4	-10/ +10	-0/ +0	-2/ +4	-2/ +4	-0/ +30	-0/ +30
Trial Day	1	2	7 ^e	15	29	30	43	57	57	58	85	120	180	181	208	270	393	393
Anchoring	-	1	1	1	1	29	29	29	57	57	57	29	1	180	180	180	180	180
SAEs ^l	X	X		X	X	X	X	X	X	X	X	X	X	X	X	X	X	
Intercurrent medical conditions ^l	X	X		X	X	X	X	X	X	X	X	X	X	X	X	X	X	
AEs leading to premature discontinuation ^l	X	X		X	X	X	X	X	X	X	X	X	X	X	X	X	X	
AESIs ^l	X	X		X	X	X	X	X	X	X	X	X	X	X	X	X	X	
Concomitant medication/vaccination	X ^m	X		X	X	X	X	X	X	X	X	X	X	X	X	X	X	
Safety laboratory (~9 mL) ⁿ	X	X			X						X				X			
Safety laboratory in case of abnormal result at previous visit (~9 mL) ⁿ							X		X				X					
Serum pregnancy test (~3 mL) ^o	X																	

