10.3 Statistical Analyses

10.3.1 General Considerations

All data obtained in this trial and documented in the eCRF will be listed and summarized with sample statistics or frequency tables as appropriate. In all tables, listings and figures, the dose groups will be reported from the lowest to the highest dose and by age group. The safety and immunogenicity analyses will be done overall and by baseline serology status for SARS-CoV-2.

The primary and secondary objectives and endpoints related to seroconversion for SARS-CoV-2 spike protein and SARS-CoV-2 neutralizing antibodies will, in addition to the immunogenicity set, be analyzed for subjects who:

- Received dose 1 and dose 2 of trial vaccine.
- Have baseline and Day 43 blood samples for immunogenicity assessment.
- Have no major protocol deviations expected to impact the immunogenicity outcomes.

A statistical analysis plan (SAP) will be prepared and finalized at the latest prior to database lock. This document will provide further details regarding the definition of analysis variables and analysis methodology to address all trial objectives and the handling of missing data.

Data on COVID-19 cases from this trial may be pooled with data from other trials investigating CVnCoV such as Trials CV-NCOV-004 and CV-NCOV-005.

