On Day 29 and Day 43 
 
The proportion of subjects seroconverting for SARS-CoV-2 spike protein antibodies, as measured by ELISA.
 
Individual SARS-CoV-2 spike protein-specific antibody levels in serum, as measured by ELISA.
 
Geometric mean titers (GMTs) of serum SARS-CoV-2 spike protein antibodies, as measured by ELISA.
 
The proportion of subjects seroconverting for SARS-CoV-2 neutralizing antibodies, as measured by an activity assay.
 
Individual SARS-CoV-2 neutralizing antibody levels in serum.
 
GMTs of serum SARS-CoV-2 neutralizing antibodies, as measured by an activity assay.
 
	Immunogenicity set. Subjects receiving an authorized/licensed COVID-19 vaccine during the course of the trial will be censored at the day after intake.  Sensitivity analysis: in addition, the primary immunogenicity analysis will be repeated for subjects who received dose 1 and dose 2 (and if eligible and received a booster dose at day 57 or day 180) of trial vaccine and for whom the baseline blood sample for immunogenicity assessment was seronegative and day 43 are available for analysis and no major protocol deviations expected to impact the immunogenicity outcomes. Subjects exposed to SARS-CoV-2 prior to the trial will be excluded. Subjects will be excluded at the time point they have been exposed to SARS-CoV-2.  Estimate of subjects seroconverted (SARS-CoV-2 spike protein-specific antibodies) with 95% credibility interval using prior beta(1.9, 0.1)  Number and percentage with exact 95% confidence intervals of subjects for who a seroconversion is observed (SARS-CoV-2 spike protein-specific antibodies)  Geometric mean of Fold Change from baseline with 95% CI (SARS-CoV-2 spike protein antibodies)  Estimate of subjects seroconverted (SARS-CoV-2 neutralizing antibody levels in serum) with 95% credibility interval using prior beta(1.9, 0.1)  Number and percentage with exact 95% confidence intervals of subjects for who a seroconversion is observed (SARS-CoV-2 neutralizing antibody levels in serum)  Geometric mean of Fold Change from baseline with 95% CI (SARS-CoV-2 neutralizing antibody levels in serum)
Secondary Safety	

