
Day 57 (only for subjects receiving the booster dose on Day 57),
 
Day 85 (only for subjects receiving the booster dose on Day 57),
 
Day 180 (only for subjects receiving the booster dose on Day 57 or Day 180),
 
Day 208 (only for subjects receiving the booster dose on Day 180), and
 
Day 393 (only for subjects receiving the booster dose on Day 180):
 
 
The proportion of subjects seroconverting for SARS-CoV-2 spike protein antibodies, as measured by ELISA.
 
Individual SARS-CoV-2 spike protein-specific antibody levels in serum, as measured by ELISA.
 
GMTs of serum SARS-CoV-2 spike protein antibodies, as measured by ELISA.
 
	
Immunogenicity set. Applicable for subjects who received a booster dose at day 57 or day 180. Subjects receiving an authorized/licensed COVID-19 vaccine during the course of the trial will be censored at the day after intake.
 
Sensitivity analysis: In addition, the secondary immunogenicity endpoint will be repeated for subjects who received dose 1 and dose 2 (and if eligible and received a booster dose at day 57 or day 180) of trial vaccine and for whom the baseline blood sample for immunogenicity assessment and day 43 are available for analysis and no major protocol deviations expected to impact the immunogenicity outcomes. Subjects receiving an authorized/ licensed vaccine during the course of the trial will be censored at the day after receiving the authorized/ licensed vaccine. Subjects exposed to SARS-CoV-2 prior to the trial will be excluded. Subjects will be excluded at the time point they have been exposed to SARS-CoV-2.
 
Estimate of subjects seroconverted (SARS-CoV-2 spike protein-specific antibodies) with 95% credibility interval using prior beta(1.9, 0.1)
 
Number and percentage with exact 95% confidence intervals of subjects for who a seroconversion is

ENDPOINTS (subject level)	ESTIMANDS (population level)

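### The SAP gives two conflicting definitions of the sensitivity immunogenicity set; neither is the protocol's, and the 14-day rule in SAP 12.9.3 can drop subjects sampled within the permitted Day 43 window

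*SAP*

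**What the plan says.** Protocol 10.3.1 adds an analysis of the seroconversion endpoints in a restricted group, alongside the immunogenicity set. Subjects must have had both primary doses, must "Have baseline and Day 43 blood samples for immunogenicity assessment", and must have no major deviation expected to affect immunogenicity. It sets no minimum time from dose 2 to the sample and no condition on serostatus or exposure.

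The SAP describes the corresponding analysis in two places.

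- **SAP 9.4, primary endpoints:** subjects "for whom the baseline blood sample for immunogenicity assessment was seronegative and day 43 are available for analysis". Those exposed to SARS-CoV-2 before the trial are excluded, and those exposed during it are excluded from that time point.
- **SAP 9.4, secondary endpoints:** subjects "for whom the baseline blood sample for immunogenicity assessment and day 43 are available for analysis", with the same exposure exclusions but no explicit requirement of a seronegative baseline.
- **SAP 12.9.3:** does not name Day 43. For the two-dose regimen it asks for a baseline sample and "one sample at least 14 days after receiving the second dose", no exposure before the trial or before the endpoint is evaluated, and no deviation affecting the immunogenicity measurement (the word major is absent).

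The Day 43 visit is set in Protocol Table 1. The relevant rows read "Visit Window (days) n/a -0/ +0 -0/ +0 -2/ +4 -2/ +4 -0/ +0 -2/ +4", "Trial Day 1 2 7 ^e 15 29 30 43" and "Anchoring - 1 1 1 1 29 29 29".

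SAP 6.1, which lists changes from the protocol, mentions only the cell-mediated immunity data and asymptomatic infection.

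**The concern.** There are two separate problems.

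First, the 14-day minimum does not fit the visit schedule. The Day 43 visit may take place up to two days early, so a sample that fully complies with the protocol can fail the SAP rule. The rule decides entry by subject. A subject who fails it loses the Day 29 result from this analysis as well as the Day 43 result.

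Second, a programmer cannot satisfy SAP 9.4 and SAP 12.9.3 together, because one requires a Day 43 sample and the other a sample after a minimum interval. Whichever is followed, the protocol's set is not produced: both SAP versions remove previously exposed subjects, whom the protocol keeps.

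The losses would also be hard to see. SAP 12.9.3 keeps the table N at the full immunogenicity set, SAP 9.5 does not define the sensitivity set as a named population, and SAP 12.1 lists reasons for exclusion from analysis sets without tabulating them.

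**Working it through.** **1. Interval from dose 2 to the Day 43 sample.** The window, day and anchoring rows of Table 1 each have 18 entries, and Day 43 is the seventh. Its window is -2/+4 and its anchor is Day 29, taken here as the actual day of dose 2.

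- Nominal interval: 43 − 29 = 14 days
- Earliest: 14 − 2 = 12 days
- Latest: 14 + 4 = 18 days

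Of the 7 permitted days, days 12 and 13 fail the 14-day rule: 2/7 = 28.6%. A visit exactly on schedule passes.

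The booster version of the rule raises no such conflict. Days 85 and 208 each fall 28 − 2 = 26 to 28 + 4 = 32 days after the booster.

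**2. The definitions side by side.**

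| Source | Sample after dose 2 | Serostatus or exposure condition |
|---|---|---|
| Protocol 10.3.1 | Day 43 | None |
| SAP 9.4, primary | Day 43 | Seronegative baseline; exposed subjects excluded |
| SAP 9.4, secondary | Day 43 | Exposed subjects excluded |
| SAP 12.9.3 | Any, at least 14 days after dose 2 | Exposed subjects excluded |

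**3. Who is at risk from the 14-day rule.** A later sample rescues a subject sampled on day 12 or 13. Under the version 3.0 footnotes to Table 1, later immunogenicity samples are scheduled only for the 6 µg groups (Day 180) and for boosted subjects, whose pre-booster samples fall at a nominal 57 − 29 = 28 or 180 − 29 = 151 days after dose 2.

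- Planned CVnCoV subjects: 603
- On 6 µg: 11 + 12 = 23
- Boosted: 30 in Group 3 and 30 + 30 in Group 4 = 90
- No later scheduled sample: 603 − 23 − 90 = 490
- Cross-check on unboosted 12 µg subjects: 60 + 30 + 200 + 200 = 490

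**4. Number lost.** The documents do not give the share of visits on days 12 and 13. The assumed range is 0% to 28.6%, the upper end being an even spread over the window.

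- Spike ELISA: 490 × 0 = 0 to 490 × 2/7 = 140
- Neutralizing antibody, measured only in the initial phase: (60 + 30) × 2/7 ≈ 26 at most

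**5. Effect on precision.** SAP 10.5.10 takes the estimate as (x + 1.9)/(n + 2) and the interval from the 2.5% and 97.5% quantiles of Beta(x + 1.9, n − x + 0.1).

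- The plan's own figure (Protocol Table 6): n = 200, x = 190 gives 191.9/202 = 95.0%, interval 91.6–97.6. It reproduces.
- Maximum assumed loss: 200 × 5/7 ≈ 143. With x = 136, 137.9/145 = 95.1%, interval 91.1–98.0.

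The width grows from 6.0 to 6.9 percentage points.

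**The case against.** The strongest reply is that this is a mismatch of wording with little consequence. The trial is descriptive, the main analysis on the immunogenicity set has no interval rule, and a minimum interval after dose 2 is a defensible choice for a per-protocol-type set. Protocol 10.3.1 leaves analysis details to the SAP. All of that stands, and it limits the size of the point. It does not explain why SAP 9.4 and 12.9.3 differ, or why SAP 6.1 is silent.

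Four stronger readings are tempting, and the documents do not support them.

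- *This set is the only check on the primary results.* SAP 12.9.1 already shows the main results overall and by baseline serostatus, at any, 2-fold and 4-fold increase, with credibility and exact confidence intervals. Baseline-seropositive subjects are therefore lost from the sensitivity set only.
- *Subjects with no Day 43 sample distort the Day 43 results.* SAP 12.9.3 does admit such a subject on a later sample, but it bases seroconversion rates on the n at the time point, and SAP 10.3 rules out imputing missing observations. Such a subject adds nothing at Day 43, although the Day 29 result would be counted.
- *All 580 subjects on 12 µg are exposed to the loss.* The 90 planned boosted subjects have later qualifying samples.
- *The primary estimates are biased.* Nothing in the documents shows that subjects seen on days 12 and 13 differ enough to matter, and the main analysis includes them.

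**Conclusion.** The point holds as a contradiction within the SAP and an undeclared departure from the protocol. Its effect is confined to the sensitivity analysis. Following SAP 12.9.3 as written drops compliant subjects whose only sample after dose 2 was taken on day 12 or 13. Following either SAP section drops previously exposed subjects. The analysis specified in Protocol 10.3.1 is not produced under either.

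The 14-day rule removes between 0 and about 140 of roughly 490 planned unboosted 12 µg subjects. This rests on planned numbers, on the version 3.0 sampling schedule, and on an assumed 0% to 28.6% of visits falling on days 12 and 13. Visits clustering on the target day would put the true figure well below the upper end. Day 180 samples drawn under earlier protocol versions would also reduce it. Even at the upper end the interval widens by less than one percentage point at n = 200. The matter should be corrected because the correction is cheap and the set is otherwise ambiguous; the main conclusions are not at risk.

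**What to change.** Use one definition in SAP 9.4 and SAP 12.9.3 that matches Protocol 10.3.1: doses 1 and 2 received, baseline and Day 43 visit samples available, and no major deviation expected to affect immunogenicity. State that any Day 43 sample within the Table 1 window (12 to 18 days after dose 2) is accepted. The protocol text does not spell this out, so it should be written down as a clarification. Present the results overall and by baseline serostatus.

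Keep the SARS-CoV-2-naive analysis as a second set with its own label. If the 14-day minimum is wanted there, list it and the exposure exclusion in SAP 6.1 with the reason, and report how many subjects each rule removes.

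The cost is SAP wording and one extra set of tables. No data collection changes. The trade-off is that the first set will include some samples taken one or two days earlier than SAP 12.9.3 would allow.

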#### 12.9.4 Exploratory Immunogenicity

Cell-mediated immune (CMI) response

On Day 1, Day 29, and Day 43 in peripheral blood mononuclear cells (PBMCs) in a subset of subjects:

The frequency and functionality of SARS-CoV-2 spike-specific T-cell response after antigen stimulation.

The CMI data will be listed only.

Innate immune response

*On Day 1 and Day 2 in a subset of subjects:*

Serum cytokine concentrations will be presented as descriptive summary with change from baseline. The following concentrations will be included: APRIL/TNFSF13, BAFF/TNFSF13B, CCL4/MIP-1 $\beta$ , CD40L, FasL, CXCL11 /I-TAC, ICAM-1, IFN- $\beta$ , IL-13, IL-17A, IL-5, IP-10/CXCL10, MCP-1/CCL2, MCP-4/CCL13, MDC/CCL22, MICA, CXCL9/MIG, MIP-1 $\alpha$ /CCL3, SCF, CD62L/L-selectin, INF- $\gamma$ , IL-1 $\alpha$ , IL-6, IL-10, CXCL13, INF $\alpha$ , IL-2, IL-4, IL-12p70, and TNF $\alpha$ .

#### 12.9.5 Additional Exploratory Analysis

Evaluation of infection:

Number and percentages of subjects with virologically-confirmed SARS-CoV-2 infection as measured by reverse transcription polymerase chain reaction (RT-PCR) at clinically determined time points throughout the trial. This analysis will be performed on the safety set.

Number and percentages of subjects with asymptomatic SARS-CoV-2 infection as measured by serology and RT-PCR test at predefined time points.

- The definition of SARS-CoV-2 infection as measured by serology and RT-PCR results before and during the trial is outlined in sections 10.6.3.
- Subjects with a COVID-19 disease symptoms are excluded. Exclusion is based on COVID-19 cases classified as AESI. Adjudicated cases are also excluded.

This analysis will be performed on the immunogenicity set.

### 12.10 Other Safety Analyses

#### 12.10.1 Laboratory Data

Blood samples for determination of hematology, clinical biochemistry and coagulation will be analyzed on Day 1, 2, 29, 85, 180 and 208. In case of abnormal results additional analyses will take place.

All laboratory data will be summarized in International System (SI) units. The conversion factors from conventional to SI units will be documented in the Local Lab Conventions document for this study.

Laboratory data will be graded according with the United States Food and Drug Administration (FDA) toxicity grading scale [1].

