Urine pregnancy test ^o	X				X				X ^g				X ^g					
TSH, thyroid antibodies, ANA (~3 mL) ^o	X																	
Nasopharyngeal swab collection for RT-PCR testing ^q	X																	
Immunogenicity^r																		
ELISA (serum) (~12 mL) ^s	X ^t				X ^t		X		X ^t		X		X ^{t,v}		X		X	
Only in subjects in the initial phase of the trial: SARS-CoV-2 neutralizing activity (serum) (~12 mL)	X ^t				X ^t		X		X ^t		X		X ^{t,v}		X		X	

Visit Number	Primary Vaccination Period								Booster Vaccination Period								End of Trial	
	1 ^a	2	Phone contact		3	Phone contact	4	Phone contact ^b	5 ^c	Phone contact ^c	6 ^c	Prompt	7	Phone contact ^d	8 ^d	Prompt	Phone contact	9 ^w
Visit Window (days)	n/a	-0/ +0	-0/ +0	-2/ +4	-2/ +4	-0/ +0	-2/ +4	-2/ +4	-2/ +4	-0/ +0	-2/ +4	-2/ +4	-10/ +10	-0/ +0	-2/ +4	-2/ +4	-0/ +30	-0/ +30
Trial Day	1	2	7 ^e	15	29	30	43	57	57	58	85	120	180	181	208	270	393	393
Anchoring	-	1	1	1	1	29	29	29	57	57	57	29	1	180	180	180	180	180
Subset of subjects from each CVnCoV group at predefined site(s): Cell-mediated immunity (~40-64 mL) ^u	X ^t				X ^t		X											
Subset of subjects from each CVnCoV group at predefined site(s): Cytokine assessment (serum) (~6 mL)	X ^t	X																
Maximum total blood volume (mL)	109	15			73		73		33		33		33		33			33
Trial end																		X

AE: adverse event; AESI: adverse event of special interest; ANA: antinuclear antibody; ECG: electrocardiogram; ELISA: enzyme-linked immunosorbent assay; Ig: immunoglobulin; RT-PCR: reverse transcription polymerase chain reaction; SAE: serious adverse event; TSH: thyroid-stimulating hormone

- Procedures to establish subject eligibility may be performed within 21 days prior to trial vaccine administration. If all information to establish eligibility is available, these procedures can be done on the same day including the trial vaccine administration. Eligibility criteria need to be reviewed on the day of vaccination prior to trial vaccine administration.
- Phone contact on Day 57 is not required for subjects receiving an open-label booster vaccination on Day 57.
- This will only take place for subjects receiving an open-label booster vaccination on Day 57.
- This will only take place for subjects receiving an open-label booster vaccination on Day 180.
- Phone contact can be made on Day 7 at the site's discretion to review the eDiary with the subject, but is not mandatory, and does not replace other scheduled phone contacts

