9.1.3 Safety Laboratory Assessments

Blood samples for determination of hematology (complete blood count, including differential and platelets), clinical biochemistry, and coagulation will be analyzed as indicated in the Schedule of Activities. An overview of the safety laboratory tests is provided in Appendix 3.

In addition, a blood sample for serum pregnancy testing will be taken from women of childbearing potential on Day 1 prior to vaccination to establish eligibility. Urine pregnancy tests will be performed before each vaccination, unless the serum pregnancy test was performed less than 3 days before and yielded a negative result.

Laboratory data will be graded according with the United States Food and Drug Administration (FDA) toxicity grading scale [33]. Any institutional normal reference ranges should be provided to demonstrate that they are appropriate.

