##### 12.10.1.1 Hematology

Hematology parameters include Leukocytes (WBC), Erythrocytes (RBC), Hemoglobin, Hematocrit, Ery. Mean Corpuscular Hemoglobin (MCH), Ery. Mean Corpuscular HBG Concentration (MCHC), Ery. Mean

Corpuscular Volume (MCV), Platelets, Neutrophils (Absolute), Lymphocytes (Absolute), Monocytes (Absolute), Eosinophils (Absolute), Basophils (Absolute), Reticulocytes (Absolute), Neutrophils/Leukocytes (%), Lymphocytes/Leukocytes (%), Monocytes/Leukocytes (%), Eosinophils/Leukocytes (%), Basophils/Leukocytes (%), Reticulocytes/Erythrocytes (%).

Hematology parameters will be summarized (n, mean, SD, median, Q1, Q3, minimum and maximum), including change from baseline at each visit and by group. In addition, shift tables summarizing the shift including baseline, minimum and maximum post baseline values and last value will be presented. In addition, all parameters will be presented in a line plot for all planned visits.

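### SAP 12.10.1 lists Day 180 as a planned laboratory day, but the protocol takes that sample only after an abnormal result, and the SAP has no rule for such repeats in its tables

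*SAP*

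**What the plan says.** - **SAP 12.10.1** names six laboratory days without conditions: "Blood samples for determination of hematology, clinical biochemistry and coagulation will be analyzed on Day 1, 2, 29, 85, 180 and 208". The next sentence adds that abnormal results lead to further analyses. It gives no days for these and no rule for tabulating them.
- **Protocol 9.1.3** makes the schedule table govern: samples "will be analyzed as indicated in the Schedule of Activities".
- **Protocol Table 1** has two safety laboratory rows. The routine row is marked on Days 1, 2, 29, 85 and 208. The second row, labelled "Safety laboratory in case of abnormal result at previous visit", is marked on Days 43, 57 and 180.
- **Table 1 footnotes** restrict who attends the later visits. For the Day 57 visit and Day 85: "This will only take place for subjects receiving an open-label booster vaccination on Day 57". For Day 208: "This will only take place for subjects receiving an open-label booster vaccination on Day 180". Day 180 carries no such limit in the Synopsis visit list, so all subjects attend it.
- **SAP 12.10.1.1 to 12.10.1.3** ask for three displays. The hematology wording is typical: descriptive statistics "including change from baseline at each visit and by group"; "shift tables summarizing the shift including baseline, minimum and maximum post baseline values and last value will be presented"; and "all parameters will be presented in a line plot for all planned visits".
- **SAP 6.1**, which lists changes from the protocol, does not mention laboratory timing.

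**The concern.** A programmer working from the SAP would treat Day 180 as a planned laboratory visit and build a table row and a plot point for it. A reader would take these as results for the whole cohort, because everyone attends that visit. Under the protocol, the values come only from subjects whose previous result was abnormal. A departure from baseline at Day 180 could then reflect who was sampled and not what the vaccine did.

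The shift tables have a related problem. They take the minimum, maximum and last post-baseline value over whatever samples exist. A subject with triggered repeats has more chances to reach an extreme, and that subject's last value comes later than the last value of a subject with none. For an unboosted subject with normal Day 29 results, the scheduled post-baseline values are Days 2 and 29 only, yet nothing in the table would say so.

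**Working it through.** **1. Day lists side by side**

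| Day | SAP 12.10.1 | Table 1 routine row | Table 1 repeat row | Who attends |
|---|---|---|---|---|
| 1, 2, 29 | yes | yes | no | all |
| 43 | no | no | yes | all |
| 57 (visit) | no | no | yes | Day 57 booster only |
| 85 | yes | yes | no | Day 57 booster only |
| 180 | **yes** | **no** | **yes** | all |
| 208 | yes | yes | no | Day 180 booster only |

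The SAP has six days and the routine row has five. Day 180 is the difference.

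**2. Check that the table is read correctly**

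The protocol states a maximum blood volume of 435 mL, or 279 mL without the cell-mediated immunity and cytokine samples. The visit volumes in Table 1 reproduce both:

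- 109 + 15 + 73 + 73 + 33 × 5 = 435 mL
- 435 − (64 + 40 + 40) − (6 + 6) = 279 mL

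By component, Day 180 is 12 (ELISA) + 12 (neutralization) + 9 (laboratory) = 33 mL, which is one laboratory draw. The eight visits with a mark in either laboratory row (five routine, three repeat) each carry 9 mL for it. These are maximum volumes, so they show where a draw can occur. Only the row label shows which draws are conditional. One item does not fit: Day 393 is given 33 mL, but its marked samples add to 24 mL. That does not bear on Day 180.

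**3. Who supplies a Day 180 value**

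Take the previous visit to be the last site visit:

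- Unboosted subjects and Day 180 booster recipients: the previous visit is Day 43, where a scheduled sample exists only after an abnormal Day 29 result. A Day 180 value therefore needs abnormal results on Days 29 and 43.
- Day 57 booster recipients: the previous visit is Day 85, a routine sample. A Day 180 value needs an abnormal Day 85 result.

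**4. Routine samples after the Day 29 visit** (Protocol Tables 2 and 5)

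- CVnCoV subjects: 11 + 12 + 90 + 90 + 200 + 200 = 603
- Booster recipients: 30 (Group 3, Day 180) + 30 (Group 4, Day 57) + 30 (Group 4, Day 180) = 90
- Unboosted: 603 − 90 = 513, and 513/603 = 85.1%
- Controls: 10 + 10 + 40 = 60, none boosted

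The 513 and the 60 have no routine scheduled sample after Day 29. The 90 have one each, after the booster.

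**5. Why the distortion cannot be sized**

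The trigger could mean outside the normal range (the classification in Protocol 10.3.5.1), clinically significant (the test for an adverse event in Protocol Appendix 10) or graded on the FDA scale (SAP 12.10.1). As an illustration, assume each parameter is out of range in 5% of subjects, independently. These figures are not in the documents. If one parameter counts, 5% are repeated on Day 43. If any of the 20 + 18 + 3 = 41 SAP parameters counts, 1 − 0.95^41 = 87.8% are. The first gives a small, heavily selected group and the second nearly the whole cohort.

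**The case against.** The strongest reply is that little is hidden:

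- The SAP reports n with each by-visit summary, so a small Day 180 group would be visible.
- Protocol 10.3.5.1 lists all laboratory values and lists abnormal ones separately.
- Clinically significant abnormalities are recorded as adverse events, AESIs are collected throughout, and a liver-investigations query is tabulated.
- The line plots cover planned visits only. On the SAP's own list this leaves out Days 43 and 57, so the plot problem is mainly Day 180.
- The trial is descriptive. Laboratory values are not a listed primary endpoint in Protocol 4.2.1, and the SAP places them under other safety analyses.

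All of this stands and limits the weight of the point. It does not remove the error. A visible n does not tell the reader that those subjects were chosen for abnormal results, and no listing corrects a shift table that mixes two kinds of sample. The SAP 12.0 default display by dose does not help either: for unboosted subjects, a dose 2 column would hold only triggered or investigator-ordered values.

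Table 1 is also imperfectly extracted. In the vaccine-administration row, the last mark falls under a phone contact. The two laboratory rows, however, land on site visits and agree with the visit volumes.

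**Conclusion.** The point holds and is minor. SAP 12.10.1 misstates Day 180 as planned, and its tables have no rule for triggered samples. The affected outputs are the Day 180 by-visit summary, the Day 180 plot point and the minimum, maximum and last-value shifts.

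Four stronger readings are tempting, and the documents do not support them:

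- *The SAP removes laboratory follow-up after dose 2.* The gap comes from the protocol's sampling design, and no SAP edit can fill it.
- *No sample at all exists after dose 2.* Protocol Appendix 3 allows additional tests at any time, so the counts concern routine scheduled samples only. They run from the Day 29 visit because the laboratory row does not say that the draw precedes dose 2. The pre-vaccination footnote is attached to the immunogenicity rows.
- *The Day 180 results are biased by a known, large amount.* The trigger is undefined, and the share repeated could be small or nearly complete.
- *The primary safety result is compromised.* Laboratory values are not among the listed primary endpoints.

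The counts assume planned enrolment and full booster uptake.

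**What to change.** In SAP 12.10.1:

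1. Give the routine days as 1, 2 and 29, Day 85 (Day 57 booster only) and Day 208 (Day 180 booster only). Label Days 43, 57 and 180 as triggered repeats.
2. Leave triggered repeats out of the by-visit summaries and line plots. Show them in a separate table with the number sampled.
3. Give worst-value shifts by interval: before dose 2, dose 2 to booster (or to end of follow-up if unboosted), and after booster. Use the number sampled as the denominator. Add a note that unboosted subjects (513 of 603 CVnCoV and all 60 controls, as planned) have no routine scheduled sample after the Day 29 visit.

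The cost is an edit to one SAP section and a few table shells, with no new data. Samples not taken after dose 2 cannot be recovered, so that part remains a stated limitation.
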